1.2.2 Effects and risks of mammography screening in the risk-based arm

We will describe here the potential benefits and risks to be derived by participants randomized to the risk-based arm.

1.2.2.1 Potential benefits

As previously demonstrated, increased mammographic screening intensity (up to yearly mammogram) has been clearly demonstrated as to increase screening sensitivity. It is currently used in high-risk situations, such in women previously treated for breast cancer, atypical lesions, or previous chest wall irradiation, as well as high risk genetic conditions, together with MRI. Such MRIs have been demonstrated as highly efficient for reducing the risk of advanced breast cancer among high-risk individuals.

Decrease in the incidence of advanced breast cancers

We expect a decrease in the incidence of stage 2 and higher breast cancers, which will concern women identified at average risk and aged 40-50, or at high-risk.

According to our assumptions (Table below - based on “no screening” before 50 and mammogram every 2 years), among 530 women overall expected to develop breast cancer at 4 years in one arm (among 42,500 participants), a risk-based strategy will increase the screening intensity in 329 of the women who are expected to develop breast cancer (light green).

We should therefore avoid 50 stages 2 or higher breast cancers in women who will get more screening than they would have in the standard arm.

MyPeBS		women aged 40-49 (25%)		women aged 50-59 (45%)		women aged 60+ (30%)	
risk level	average risk in level	Expected distribution	Expected cancers at 4y	Expected distribution	Expected cancers at 4y	Expected distribution	Expected cancers at 4y
Low	0,8%	60%	41	28%	34	15%	12
Average	1.4%	25%	30	33%	71	30%	43
High	2.3%	15%	29	40%	141	55%	129
TOTAL		10 625	100	19 125	246	12 750	184

Decrease of the incidence of false positive recalls and overdiagnosis among women classified as low-risk

In women identified as having a low risk, we expect to reduce the risk of false positives findings (around 300), as well as overdiagnosis (around 5), together with the levels of the stress/anxiety induced by regular mammograms. No impact is expected on radio-induced cancers in such short term but this theoretical benefit exists.

Decrease in breast cancer risk through risk reduction measures in women identified at high-risk

Although this will not be a directly measurable effect, we can expect that women identified at high risk will consider risk-reduction measures, which may contribute in a long-term breast cancer risk reduction.

1.2.3 Potential risks from the participation in the risk-based arm

Small increase in stage 2 or higher breast cancers in women identified at low-risk

Such women are at low but not null breast cancer risk. 87 breast cancers are expected in women for whom only 4-yearly mammogram will be planned (low-risk), but for 41 of these women, the standard is an absence of mammogram since they are aged 50 or less. Only 46 cancers are expected in low risk women for whom the current standard would be to do bi-yearly mammogram, and who will get 4-yearly mammogram instead (light orange in the table above). According to the most pessimistic estimation an excess of 5 stage 2 or higher breast cancers may therefore be observed in these low-risk women.

This potential increase must be prevented by specific dedicated measures including information of participants in this group, repeated and careful breast awareness and annual reassessment of risk.

Increase in false positive recalls and overdiagnosis in high-risk women and in women less than 50 undergoing end of study mammogram

Overall, we should observe an increase in false positive recalls among these patients. The rate of such events is hardly evaluable, since such recalls are proportionally less frequent in women undergoing yearly mammograms than those getting bi-annual screening. It could be around 500 additional false positive findings. As well, there should be an increase in potentially overdiagnosed breast cancers, although such events appear rarer among high-risk individuals.

Increase in anxiety from risk identification and from additional screening images in the high risk women

It might happen, but is not certain, that the identification of a high-risk situation can cause anxiety or distress. From previous studies, it seems this anxiety is transient and low. This will be carefully scrutinized throughout the study with interim analyses of psychological safety.

1.3 Study population

This study addresses women from the general population aged from 40 to 70 years old, who will be invited by the standard screening program to perform a breast cancer screening (potential participants' information on the trial by participating regional screening structures: 3 in Belgium, 3 in UK, 4-6 in Italy, 11 in Israel, 40 in France) or self-referral in a participating region.

2. STUDY OBJECTIVES

2.1 Primary objective

The primary objective is to show non-inferiority of the risk-stratified screening strategy in terms of incidence rate of breast cancer of stage 2 and higher (2+), compared to standard screening.

2.2 Secondary objective(s)

(ALL AT 4 YEARS/DURING INTERVENTION PERIOD UNLESS OTHERWISE INDICATED)

1. The key secondary objective, if non-inferiority is shown, is **to demonstrate superiority** of the risk-based screening arm to reduce the incidence rate of stage 2+ breast cancer, compared to standard screening.

2. To compare the rate of morbidity between the two arms, in terms of false positive imaging findings and benign biopsies
3. To describe the psycho-social characteristics of the population accrued and evaluate the psycho-social impact of each strategy (acceptance, observance, anxiety, distress, satisfaction, decisional regret, etc.)
4. To evaluate the costs and cost-effectiveness of each strategy
5. To evaluate the stage-specific incidence of breast cancer of any stage in each arm
6. To estimate overdiagnosis and overtreatment rates in risk-based screening and standard screening arms
7. To compare the rate of false negative mammograms and interval cancers between arms
8. To evaluate superiority of risk-based screening in terms of breast cancer-specific mortality at 10-years and 15-years in MyPeBS and in a combined analysis of the Wisdom and MyPeBS studies
9. To evaluate the added value of tomosynthesis (TS) in the detection of stage 2+ breast cancers
10. To evaluate the incidence of all stage and stage 2+ breast cancers at 10- and 15-year follow-up
11. To evaluate the incidence of stage 2+ breast cancer in risk-based screening in women aged 40-50 years old as compared to standard screening
12. To evaluate the rate of breast cancers discovered at second reading in each arm
13. To evaluate false positive imaging findings and benign breast biopsy rates in women classified in the low risk category in risk-based arm

EXPLORATORY OBJECTIVES (ALL AT 4 YEARS/DURING INTERVENTION PERIOD UNLESS OTHERWISE INDICATED):

1. To evaluate the added value of ultra-sound in the detection of stage 2+ breast cancers in each arm
2. To describe and compare between the arms, the rates of breast cancer predicted at 10- and 15-year, metastatic risk >10% using validated clinical-pathological predictors and the rates of cancers requiring chemotherapy
3. To explore the efficacy and morbidity of risk-based screening versus standard screening in subgroups (including country, risk and age categories)
4. To refine long-term breast cancer risk prediction scores through improvement of existing scores and/or description of new risk scores including clinical, imaging and/or genotyping characteristics and prediction of different breast cancer subtypes
5. To refine the breast cancer risk prediction value of mammographic and other images
6. To evaluate our ability to predict for poor psycho-social impact and low compliance to screening
7. To evaluate the accuracy (sensitivity and specificity) of SNPs to predict for the presence of a founder mutation of BRCA1 or BRCA2 ((BRCA1 (185delAG and 5382insC), and BRCA2 (6174delT))

3. STUDY DESIGN AND ENDPOINTS

3.1 Description of the Study Design

MyPeBS is a European randomized open-label, multicentric, study assessing the effectiveness of a risk-based breast cancer screening strategy (using clinical risk score and polymorphisms) compared to the standard of care in terms of detection of high-risk cancers (**according to current national guidelines in each country**), in detecting stage 2 + breast cancers.

Our overall objective is to compare the effectiveness of two Breast Cancer Screening strategies:

[figure not shown]
- **Standard strategy:** Current standard of care in participating countries where women are invited to a common schedule of screening mammograms performed once every 2-3 years starting from ages 40-50 up to ages 69-70, while the already identified very high risks individuals (at most 5%) have more intense personalized follow-up;

- **Risk-based strategy:** Extension of the personalized screening strategy, in which women are invited to radiological examinations scheduled according to their risk of developing breast cancer and to an individually-defined plan, for the whole population.

Our primary hypothesis is that risk-based screening will be **non-inferior** in terms of overall stage 2+ breast cancer incidence. We hypothesize it should also be **superior (decreased incidence of stage 2+ breast cancer); equally or more cost-effective;** but more acceptable (resulting in a wider coverage and a better compliance) **than standard screening.**

Women will be differentially screened for 4 years and then, after an end-of-study mammogram, they will return to the routine screening practice. The main endpoint is measured at the end of the four years of intervention. Furthermore follow-up data will be collected for 15 years from study entry of long-term cumulative breast cancer incidence and breast cancer specific survival.

General design

3.1.1 Selection

Women meeting inclusion criteria in a region participating in the study will be informed of the trial by the regional referral screening organization. Some women may self-refer to an including center or will be proposed the study while consulting for a pre-planned screening event or for a regular clinical visit to a GP or radiologist.

Women will only be able to enter the study if they live in a participating region/area from a participating country, due to organization constraints.

3.1.2 Accrual visit

Women interested in participating in the study will have a dedicated visit with an investigator in a participating center. During this visit, women will get all necessary oral and written information regarding current breast cancer screening (benefits and disadvantages), and regarding breast cancer risk, as well as the motivations, objectives, methodology, organization and logistics of the MyPeBS clinical study. They will be provided written information regarding both breast cancer screening and MyPeBS study.

Women will have a reflection time interval of 2 weeks before signing the informed consent, if they wish so.

Women who meet the inclusion criteria and are willing to participate will:

- Be created a dedicated portal entry by their accruing physician
- Be personally delivered the information on the trial by the investigator
- Be able to read the informed sheet and sign the informed consent form online on their personal portal in the study
- Sign a written online informed consent form.
- Be asked to fill-in online baseline questionnaires (see Table 1 and I, schedule of activities), before the result of the randomization.

3.1.3 Randomization

Women who have signed the informed consent and fulfill all eligibility criteria will be randomized directly online by the investigator (see 3.4.2)

The results of the randomization will be immediately provided to both the investigator and the woman.

- Women randomized to the standard arm will immediately receive their personal "standard" screening schedule for the next 4 years. No other study visit with the investigator is formally planned.
- Women randomized to the risk-based arm will be asked to provide a saliva sample (see below). Their breast density will be evaluated. They will be scheduled for a second visit (physical or by telephone interview according to national/local regulations), during which they will be communicated their risk estimation and their personalized, risk-based, screening schedule/plan for the next 4 years.

3.1.4 Follow-up

Women participating in the study will be asked to comply with the protocol for 4 years from randomization, according to their schedule of screening examinations defined at study entry (standard-of care or risk-based).

A mandatory end of study mammogram is planned at 4 years

A study exit mammogram will be planned ONLY for the following women:

- women in the risk-based screening arm who have been categorized as low risk (no planned mammogram during the course of the study);

- women in the standard screening arm who had no screening mammogram during the 4-year study period given their age

These women will all have a mandatory end-of-study mammogram at 4 years

For all the other women, the last mammography scheduled during the 4-year follow-up will be considered as the end-of-study mammography.

During their 4-years participation in the study, women will be screened according to their assigned screening scheme in either arm:

BREAST CANCER SCREENING SCHEME IN THE STANDARD ARM

Standard arm (either no mammogram or mammogram(s)/1-2-3 years according to age and country – will be defined individually at entry)				
Population	40-49 (France, Belgium, UK and Israel) 40-44 (All women of Italy) 45-49 (for some women depending the region of Italy)	50-70 (UK)	50-70 (France, Belgium, Italy and Israel)	45-49 (Some regions of Italy)
Planned images	No mammogram	Mammogram* every 3 years	Mammogram* every 2 years	Mammogram* every year

RISK THRESHOLDS IN MYPEBS AND BREAST CANCER SCREENING SCHEME IN THE RISK-BASED ARM

Risk-based arm				
Risk level	Low risk	Average risk	High risk	Very high risk
Numerical definition (invasive breast cancer risk at 5-years)	< 1%	1-1.66%	$\geq 1.67\%$ and < 6%	$\geq 6\%$ at 5 years
Mammogram*	1 at end of study	Every 2 years	Yearly	Yearly
Additional	Yearly breast cancer awareness reminder	High density: US or ABUS/ 2 years	High density: US or ABUS/ year	Annual MRI until age 60

* Or Tomosynthesis + synthetic 2D if applicable in the country/center
The use of ultrasound will be conducted as in the previous table

3.2 Study Endpoints

3.2.1 Primary endpoint

The primary endpoint is the incidence rate of stage 2 + breast cancers at 4 years (UICC 2010)

3.2.2 Secondary endpoint(s)

SECONDARY ENDPOINT(S): (All at 4 years/during intervention period unless otherwise indicated):

1. Rates of false positive imaging findings and benign biopsies in each study arm
 - False positive imaging findings include BI-RADS-ACR 3, 4 and 5 (or equivalent) lesions identified on screening images and leading to the need of additional images (US, MRI...), later control or breast biopsy
 - Benign biopsies include any percutaneous or surgical breast diagnostic procedure aimed at identifying the nature of a breast image
2. Socio-psychological assessments at baseline, and then at 1 and 4 years including evaluation of: comprehension of information, acceptance of proposed screening strategy, observance, persistence, anxiety, distress, satisfaction, decisional regret (see questionnaires in table 1)
3. Crude costs, comparison of cost-effectiveness, and budget impact of each strategy
 - Crude costs are defined as full real costs per stage 2 cancer diagnosis in each arm
 - The cost-effectiveness of mammographic screening will be calculated by comparing estimated life-years and costs of breast cancer in each arm
4. Incidence of stage-specific breast cancer in each arm (including DCIS)
5. Estimates of overdiagnosis and overtreatment rates in each study arm
 - Overdiagnosed breast cancer cases are defined as cancers that would never have been diagnosed, if women had not been screened. Differential overdiagnosis can be measured comparing the cumulative incidence of breast cancer from recruitment to a reasonably long period after the end of the study intervention, i.e. longer than the expected sejour time of screen-detected cancers. Breast cancer incidence rates in each arm will be determined approximately 10 - 15 years after the end of the interventional period of the study via interrogation of databases from national health insurances and/or organized breast screening structures.
6. Rate of false negative images and interval cancers in each arm
 - False negative images: in case of diagnosis of breast cancer in women whose last screening images (including mammogram +/- US and MRI) were considered as Breast Imaging- Reporting and Data System 1 or 2 (BI-RADS 1 or 2) at 6 months maximum before diagnosis
 - Interval cancers are defined as a breast cancers diagnosed between a negative screening episode - [mammogram classified as normal (BI-RADS ACR 1 or 2 or equivalent) or abnormal mammogram but negative assessment] and the next planned mammogram
7. 10- and 15-year breast cancer specific survival in MyPeBS and in a combined analysis of the Wisdom and MyPeBS studies
8. Detection rate of stage 2+ breast cancer in women who had screening tomosynthesis (where and when available) and the rate without tomosynthesis
9. Incidence of all stage and stage 2 + breast cancers at 10- and 15-year follow-up
10. Incidence of stage 2 + breast cancer in each arm, in women aged 40-49 at inclusion
11. Rate of breast cancers identified at second reading in each arm
12. Rate of false positive imaging findings and benign breast biopsies in women classified at low risk in risk-based arm

3.2.3 Exploratory endpoints (all at 4 years/during intervention period unless otherwise indicated):

1. Percentage of breast cancers and stage 2 + cancers that were detected solely by ultrasound in each arm

2. Rate of high metastatic risk breast cancers in each arm using a validated clinical predictor
3. Subgroups analyses of incidence of stage 2 + breast cancers and any stage breast cancer, as well as false positive findings and benign biopsies in each arm (including country, risk and age groups)
4. Updated/new breast cancer risk prediction scores including clinical variables, imaging parameters and genotyping
5. Identification of updated/new imaging parameters to predict breast cancer risk
6. Identification of predictors of poor psycho-social impact and/or compliance to screening
7. Accuracy (sensitivity and specificity) of SNPs to predict for the presence of a founder mutation of BRCA1 or BRCA2 (BRCA1 (185delAG and 5382insC), and BRCA2 (6174delT))

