5. INTERVENTIONS

5.1 Trial conduct if the standard arm

In the standard arm of MyPeBS, women are screened for breast cancer according to the current national guidelines and procedures:

- Bi-yearly or tri-yearly mammogram and/or tomosynthesis starting at age 40-50, up to age 69-70 according to countries, with or without Ultrasound (US) according to breast mammographic density and ongoing guidelines.
- The current national/regional guidelines in use in the including center may be subjected to change during the trial. Guidelines and procedures in the standard arm will be updated accordingly. Current per country and per age guidelines applicable to standard arm are described in table 2.

Breast cancer risk reduction measures:

Participants in the standard arm will be informed of potential risk-reducing strategies. They will be provided written and on-line information material and encouraged to follow these predefined measures.

Participating women will receive standardized self-awareness recommendations, although they will remain free to comply with them or not.

BREAST CANCER SCREENING SCHEME IN THE **STANDARD** ARM

Standard arm (either no mammogram or mammogram(s)/1-2-3 years according to age and country – will be defined individually at entry)				
Population	40-49 (France, Belgium, UK and Israel) 40-44 (All women of Italy) 45-49 (for some women depending the region of Italy)	50-70 (UK)	50-70 (France, Belgium, Italy and Israel)	45-49 (Some regions of Italy)
Planned images	No mammogram	Mammogram* every 3 years	Mammogram* every 2 years	Mammogram* every year

* Or Tomosynthesis + synthetic 2D if applicable in the country/center

As stated, all participating countries have specific guidelines for:

- High-risk women defined as having had a previous breast cancer or high-risk situations including radiation therapy for Hodgkin's disease or atypical hyperplasia. These women will not be eligible for MyPeBS
- Very high-risk women defined as having a germline mutation of either BRCA1 or BRCA2 genes or an equivalent situation. The women already identified as such will not be included in MyPeBS

A summary of ongoing guidelines in the participating countries at the time of the final design the present protocol is shown below:

Country	Region	Age eligibility in OS	Mammographic screening frequency	2 nd reading	Ultrasound policy	Tomosynthesis policy	Other
Belgium	Brussels	50-69	2 years	Yes	Not included in program	Outside OS	No CBE
	Leuven					Within OS	

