5.2.5 Breast Cancer Screening in the risk-based arm

In the risk-based arm, women are screened in a risk-based fashion:

Screening recommendations in each risk category are as described in the Table below.

- Women identified at low risk will not have any mammogram until an end of study mammogram at 4 years.
- Women at average risk will have a mammogram every 2 years
- Women at high risk will have a yearly mammogram
- Women at very high risk will have a yearly mammogram + yearly MRI until age 60. Both shall be performed at the same time period, MRI being performed before mammogram.
- Breast US is proposed in women with dense breasts, according to national guidelines

2D digital mammogram may be replaced by tomosynthesis according to the country's, regions' and centers' policy.

Definition of risk thresholds and breast cancer screening scheme in the **risk-based** arm are summarized below:

Risk-based arm				
Risk level	Low risk	Average risk	High risk	Very high risk
Numerical definition (invasive breast cancer risk at 5 years)	< 1%	1-1.66%	$\geq 1.67\%$ and < 6%	$\geq 6\%$ at 5 years
Mammogram*	1 at end of study	Every 2 years	Yearly	Yearly
Additional	Yearly breast cancer awareness reminder	High density: US or ABUS every 2 years	High density: US or ABUS every year	Annual MRI until age 60

* Or Tomosynthesis + synthetic 2D if applicable in the country/center

The participants' screening schedules will be organized according to the date of their last previous

mammogram, as described in the Table below:

		Planned initial Mammogram/ DBT schedule		
		Every 2 years	Yearly	Yearly
Schedule of first screening mammo/DBT according to previous mammogram	No previous mammogram	immediately	immediately	immediately
	Previous mammogram < 1 year	2 years from previous one	1 year from previous one	1 year from previous one
	Previous mammogram between 1 and 2 years	2 years from previous one	immediately	immediately
	Previous mammogram > 2 years	immediately	immediately	immediately

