8.6.2 Definition and methods for other secondary end points

- False positive recalls and rates of benign biopsies will be measured as stipulated by the European Guidelines for Breast cancer screening (<http://www.euref.org/european-guidelines>, and <http://ecibc.jrc.ec.europa.eu/-/european-guidelines-for-breast-cancer-screening-and-diagnosis-the-european-breast-guidelines>)
- Socio-psychological impact of risk-based screening as compared to standard, will be evaluated using validated questionnaires, as largely described in WP5 of the whole project
- Costs and cost-effectiveness will be evaluated as largely described in WP4 of the whole project H2020 (refer to section 1.1.25)
- Underserved women will be defined using both the European Deprivation Index (EDI) and the International Standard Classification of Education (ISCED) scales, both being validated at a European level
- Interval cancer will be defined following the European Commission's definition, as a primary breast cancer, which is diagnosed in a woman who had a screening, test, with/without further assessment, which was negative for malignancy, either:

- before the next invitation to screening, or
 - within a time period equal to a screening interval for a woman who has reached the upper age limit for screening.
- Breast cancer specific survival will be defined according to the DATECAN definition (Gourgou et al)

As planned in the secondary end-points, we will perform joint analyses of MyPeBS with the WISDOM personalized breast cancer screening trial performed in California and the Midwest (PI [name], UCSF). These analyses will be performed after the primary analysis of MyPeBS (scheduled for 2025) and WISDOM (scheduled for 2020). The joint analyses will address two different objectives:

- Estimate the differential effect of stratified screening in terms of decreasing stage 2+ cancers across the two trials
- Joint analysis for long-term disease specific mortality (this will require at least 10- and 15-years of follow-up)

A joint steering committee will be set-up and a statistical analyses plan for the joint analysis using meta-analysis techniques.

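### Interval cancers and false negatives are compared between arms, but only women with an earlier negative screen can count, and allocation decides who has one

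*Protocol*

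**What the plan says.** Section 2.2, item 7, sets the objective: "To compare the rate of false negative mammograms and interval cancers between arms". Section 3.2.2, item 6, supplies the definitions. A false negative needs screening images read as "BI-RADS 1 or 2) at 6 months maximum before diagnosis". For the other measure, "Interval cancers are defined as a breast cancers diagnosed between a negative screening episode" and the next mammogram on the woman's schedule.

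Section 8.6.2 defines interval cancer again, after the European Commission, as a primary breast cancer "which is diagnosed in a woman who had a screening, test, with/without further assessment, which was negative for malignancy", with the window normally closing at the following invitation. Section 12.2 lists as safety evaluations false negatives and cancers arising between two normal mammograms. All these wordings presuppose a negative screen. None says whether a mammogram taken before randomization or at baseline qualifies, and none gives the denominator of the rate.

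The schedules differ in whom they screen. In section 5.1 the standard-arm column without any mammogram is headed "40-49 (France, Belgium, UK and Israel) 40-44 (All women of Italy"), plus women aged 45-49 in part of Italy. For the risk-based arm, section 5.2.5 says: "Women identified at low risk will not have any mammogram until an end of study mammogram at 4 years". Average-risk women there are screened every 2 years and high-risk women every year, whatever their age. Women left unscreened in either arm have a mandatory mammogram at 4 years (section 3.1.4).

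**The concern.** A comparison of randomized arms is fair when membership of the counted group does not depend on allocation. Here it does. A standard-arm woman of 45 who has never been screened and presents with a lump is neither an interval case nor a false negative. A comparable woman placed at average or high risk in the other arm is screened, and so can become either. In the opposite direction, a low-risk woman of 55 has screens in the standard arm that can be followed by an interval cancer, but no in-trial screen before the exit mammogram in the risk-based arm.

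Followed exactly as written, the endpoint can make added screening look worse in one group and withdrawn screening look better in another. It is also among the measures that section 12.2 treats as safety evaluations.

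**Working it through.** **1. Reproduce the protocol's table (section 1.2.2.1).** Expected cancers = women in age band × share in risk level × 5-year risk × 4/5.

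- Age 40-49: 10,625 × 0.60 × 0.008 × 0.8 = 40.8 (low); 10,625 × 0.25 × 0.014 × 0.8 = 29.8 (average); 10,625 × 0.15 × 0.023 × 0.8 = 29.3 (high). The table has 41, 30 and 29.
- Age 50-59, by the same formula: 34.3, 70.7, 140.8. Age 60+: 12.2, 42.8, 129.0.
- Sum 529.7, against the stated figure: "among 530 women overall expected to develop breast cancer at 4 years in one arm (among 42,500 participants". Low risk 87.3, against 87 in section 1.2.3; low risk aged 50+ 46.5, against 46.

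The table reproduces. From its rounded cells, per arm: age 50+ 246 + 184 = 430; age 40-49 100; average risk 30 + 71 + 43 = 144; high risk 29 + 141 + 129 = 299; low risk 87.

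**2. Other inputs.** Section 1.1.2 puts interval cancers at 16-35% of cancers, varying with how often women are screened. Two assumptions are not from the protocol. The first is the share under yearly screening, set either at 16% or equal to the two-yearly share. The second is the fraction u of cancers in unscreened women that surface clinically before the exit mammogram, taken as 0.5 to 1.

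**3. Average- and high-risk women aged 40-49: 30 + 29 = 59 cancers per arm.**

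- Risk-based: 59 × 0.16 = 9.4 to 59 × 0.35 = 20.7 interval cancers.
- Standard: about 0, although 59 × 0.5 = 29.5 to 59 would surface clinically.

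The arm that screens these women scores worse.

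**4. Low-risk women aged 50+: 46 cancers per arm.**

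- Standard: 46 × 0.16 = 7.4 to 46 × 0.35 = 16.1.
- Risk-based, in-trial screens only: 0, although 46 × 0.5 = 23 to 46 would surface clinically.

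The arm that withholds screening scores better. If a pre-trial negative mammogram counts, the 23-46 are counted and this group is ordered correctly, but never-screened women aged 40-49 in the standard arm still score 0.

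**5. Arm totals.** Let s2 be the two-yearly share and s1 the yearly share. Standard = 430 × s2. Risk-based = 144 × s2 + 299 × s1, plus 46 × u if pre-trial mammograms count (taking every woman aged 50+ to have one and no woman aged 40-49). All cancers not found by screening add 100 × u to the standard figure and 87 × u to the risk-based in-trial figure. Ranges run from u = 0.5 to u = 1.

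| s2 / s1 | Interval: standard | Interval: risk-based, in-trial screens | Interval: risk-based, pre-trial counts | All not screen-detected: standard | All not screen-detected: risk-based |
|---|---|---|---|---|---|
| 16% / 16% | 68.8 | 70.9 | 93.9-116.9 | 118.8-168.8 | 114.4-157.9 |
| 25% / 16% | 107.5 | 83.8 | 106.8-129.8 | 157.5-207.5 | 127.3-170.8 |
| 25% / 25% | 107.5 | 110.8 | 133.8-156.8 | 157.5-207.5 | 154.2-197.8 |
| 35% / 16% | 150.5 | 98.2 | 121.2-144.2 | 200.5-250.5 | 141.7-185.2 |
| 35% / 35% | 150.5 | 155.0 | 178.0-201.0 | 200.5-250.5 | 198.5-242.0 |

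All cancers not found by screening are fewer in the risk-based arm in every row. The interval count has the opposite sign when both schedules share one interval proportion, by a small margin if only in-trial screens count. It has the same sign at 35% / 16%. At 25% / 16% with pre-trial mammograms counted, the sign turns when 83.8 + 46 × u exceeds 107.5, that is u > 23.7 / 46 = 0.51.

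**The case against.** Interval cancers and false negatives are screening-performance indicators, conditional on a negative test by construction. The protocol adopts the European definition and nowhere claims that endpoint 6 captures every cancer that escapes screening. Cancers in unscreened women are counted elsewhere: in the primary endpoint if stage 2+, in stage-specific incidence (endpoint 4), in stage 2+ incidence at age 40-49 (endpoint 10), in the exploratory subgroup analyses, and in the Ethics and Data Monitoring Committee's review of low-risk cancers (section 12.3).

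Part of this stands: the cost of less screening in low-risk women is not hidden from the trial. But a programme indicator for women who were screened does not give a fair contrast between strategies that differ in whom they screen. The primary endpoint omits earlier stages, the incidence endpoints do not separate mode of detection, and committee review is not a comparison of arms.

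The zero for the standard arm at 40-49 is also only approximate. Some Italian regions screen yearly at 45-49, Italy is to recruit 30,000 of the 85,000 women, and prior mammography is common enough to be a stratification factor.

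Two stronger readings are tempting. A reader might infer that the risk-based arm will show 34-70% more interval cancers (201.0 / 150.5 = 1.34; 116.9 / 68.8 = 1.70). That needs one interval share for all schedules, although section 1.1.2 says the share varies with the interval. It also needs every unscreened cancer to surface before the exit mammogram, and no earlier mammograms at 40-49. At 35% / 16% with u = 1 the result is 144.2 against 150.5, with no reversal.

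A reader might also infer that false negatives penalise frequent screening, since yearly screens open up to 4 × 6 = 24 months of exposure and two-yearly screens 2 × 6 = 12. That bites only if the denominator is women. The protocol speaks of mammograms and images, states no per-woman rate, and may leave the denominator to the SAP, which is not shown.

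**Conclusion.** The concern holds for what the protocol fixes: a between-arm comparison of measures that require an earlier negative screen, when the randomized strategy determines who has one.

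Within two groups the distortion is clear. At ages 40-49 with average or high risk it is about 9-21 against about 0, out of 59 expected cancers per arm. For low-risk women aged 50+ it is none against 7-16, out of 46 per arm, if only in-trial screens count. These figures rest on the protocol's table and its 16-35% range.

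A wrong sign in the arm totals is possible but not established. It depends on whether pre-trial mammograms count, on the interval share by schedule, and on how many cancers surface before the exit mammogram. This is a secondary endpoint with no bearing on the non-inferiority or superiority tests. It should still be corrected, because no other endpoint compares cancers of all stages that screening did not find.

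**What to change.** - In objective 7 and endpoint 6, make the between-arm comparison the rate of all breast cancers not detected by a scheduled screening examination, per woman-year from randomization, in all randomized women.
- Keep interval cancers (European definition) and false negatives as descriptive performance measures by schedule, with false negatives expressed per screening examination.
- State one rule, the same in both arms, on whether a pre-trial or baseline negative mammogram counts. Section 5.2.3 makes a baseline mammogram mandatory for some risk-based women so that density can be read, so the rule should cover these explicitly.
- Reconcile the wordings in sections 3.2.2, 8.6.2 and 12.2.

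The cost is mainly endpoint wording. Mode of detection is not a listed data item, and the primary event count in section 8.2.1 includes both modes without requiring the mode to be recorded. It should be derivable from the imaging results and cancer dates in the schedule of activities and section 11.1.2, and from the cancers found outside screening that section 12.2 already collects as events of special interest. The small downside is that the headline contrast is no longer the usual programme indicator, which remains available as a descriptive figure.
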